#### **8.1.2 Sample Size**

No formal sample size estimation was performed. Up to 66 subjects will be enrolled to achieve approximately 60 completed subjects, based on an estimated drop-out rate of 10%. Subjects will be randomized 1:1 to receive DM199 or placebo, resulting in 33 enrolled subjects per treatment group. A sample size of 30 completed subjects in each treatment group is considered adequate to evaluate the safety and tolerability of DM199. Should a subject drop out, the drop out subject may be replaced by a subject assigned to the same treatment arm as the drop out subject.

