### 5.3 RANDOMIZATION AND BLINDING

After it is confirmed that all eligibility criteria have been met, subjects will be randomized in a 1:1 fashion to receive DM199 or placebo. Subjects will be considered enrolled in the study after the informed consent form (ICF) has been signed, it is determined that he/she meets all eligibility criteria, and treatment assignment is obtained from the Interactive Web Response System (IWRS). No stratification will be incorporated into the master randomization schedule.

To minimize bias, the subject and Principal Investigator will be blinded to treatment assignment. All Sub-Investigators and other members of the study team will also remain blinded except for a designated unblinded pharmacist responsible for dispensing the assigned study treatment. The study team will remain blinded until all data is collected and database lock occurs. Until this time, the unblinding may only occur via authorized use of the IWRS only if knowledge of treatment is needed to manage a subject's condition (refer to **6.5.2 Safety Unblinding**).

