### **6.5.2 Safety Unblinding**

If knowledge of treatment assignment is needed to manage a subject's condition, as in the case of an immediately reportable SAE, the Principal Investigator or designee will contact the Medical Monitor who, in consultation with the Sponsor, will grant permission to unblind the subject in accordance with the Unblinding Plan. The only exception is when a medical emergency exists and authorization cannot be immediately obtained.

If unblinding occurs, the date and reason for unblinding (but not the subject's treatment assignment) will be documented. Any subject who requires unblinding will be discontinued from further study treatment and an Early Withdrawal Visit will be completed. Subjects will not be routinely unblinded in the case of an AE.

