##### **8.1.3.1 Safety Population**

All randomized subjects who receive any amount of study treatment will be included in the Safety Population. Subjects will be summarized according to the treatment they actually received. Demographic, baseline characteristics, plasma concentrations of DM199, and Safety analysis will be conducted using the Safety Population.

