## 8.3 STATISTICAL METHODS

Data will be handled and processed according to the sponsor's representative (Novotech (Australia) Pty Ltd) Standard Operating Procedures (SOPs), which are written based on the principles of GCP.

All data collected on the eCRFs and results of central laboratory analysis will be presented in the data listings. All summaries will present the data by treatment group and overall (total subjects), as applicable.

Statistical methods will be primarily descriptive in nature. Each treatment group will be summarized separately. No formal statistical comparisons of DM199 versus placebo will be made.

The following statistical approaches will be taken:

- Continuous variables: Descriptive statistics will include the number of non-missing values (N), mean, standard deviation (SD), median, minimum, maximum. Additionally, for plasma concentrations of DM199, the coefficient of variation (CV%), geometric mean and geometric coefficient of variation (geo CV%) values may also be presented.
- Categorical variables: Descriptive statistics will include frequency counts and percentages per category.
- Imputation: No missing data will be imputed generally. The handling and presentation of plasma concentrations of DM199 below the limit of quantification (BLQ) will be discussed in the Statistical Analysis Plan.

- Confidence intervals (CIs): CIs will be two-sided and will use 95% confidence levels unless specified otherwise.
- Baseline: Baseline values will be defined as the last non-missing observation for each subject prior to the first dosing of study medication (i.e. start of infusion on Day 1).

Detailed statistical methods will be provided in a separate Statistical Analysis Plan (SAP) prior to data base lock.

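### Does same-arm replacement of drop-outs undermine the 1:1 randomisation or the cap of 66 subjects?

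*Combined protocol and SAP*

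**What the plan says.** Section 8.1.2 states that no formal sample size estimation was done and then sets the size: "Up to 66 subjects will be enrolled to achieve approximately 60 completed subjects, based on an estimated drop-out rate of 10"%. It continues: "Subjects will be randomized 1:1 to receive DM199 or placebo, resulting in 33 enrolled subjects per treatment group", and calls 30 completers per group adequate. Its last sentence adds the replacement option: "the drop out subject may be replaced by a subject assigned to the same treatment arm as the drop out subject". Section 2.3 repeats all of this; the synopsis gives the sample size text without the replacement sentence.

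Section 5.3 says that "subjects will be randomized in a 1:1 fashion to receive DM199 or placebo". A subject counts as enrolled once consent is signed, eligibility is confirmed and the IWRS has returned an assignment. The subject, the investigators and the study team are blinded, with a designated pharmacist as the exception. The section does not mention replacements.

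Section 6.5.2 limits unblinding to cases where the arm must be known to manage the subject, and adds: "Any subject who requires unblinding will be discontinued from further study treatment and an Early Withdrawal Visit will be completed".

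On analysis, section 8.1.3.1 says: "All randomized subjects who receive any amount of study treatment will be included in the Safety Population". Section 8.1.3 defines no completer population. Section 8.3 says: "No formal statistical comparisons of DM199 versus placebo will be made".

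**The concern.** Three things catch the eye.

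1. **Two allowances for one loss.** The 66 is already 60 inflated by 10%. A replacement rule on top looks like a second provision, and the text does not say whether replacements count within the 66. If they do not, the cap is broken. If they do, 33 per group no longer follows automatically.
2. **An arm that is not drawn at random.** A same-arm replacement takes its arm from an earlier subject's outcome after randomisation. Section 5.3 describes only 1:1 assignment and gives no separate route.
3. **A possible route to a known assignment.** Section 6.5.2 sends unblinded subjects off treatment and to an Early Withdrawal Visit. If such a subject counts as a drop-out and is replaced, someone at the site may know the arm before the replacement enters.

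At stake would be the blind behind investigator-judged AE causality, which is part of the primary endpoint, and behind the three stroke scales rated by the study team.

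**Working it through.** **Inputs** (sections 2.3 and 8.1.2): cap 66, 33 per group, target about 60 completers, 30 per group, drop-out 10%. Assumption: drop-outs are independent and equally likely in both arms.

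**The plan's own figure.** 60 × 1.10 = 66 and 30 × 1.10 = 33, as stated. Dividing instead gives 60/0.90 = 66.7 and 30/0.90 = 33.3, close enough for an approximate target. Expected completers are 66 × 0.90 = 59.4, or 33 × 0.90 = 29.7 per group. So the 66 does include the drop-out allowance.

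**Inside or outside the cap.** A replacement has consented, is eligible and gets an IWRS assignment, which is what section 5.3 means by enrolled. It therefore counts towards the 66. The other reading, with replacements added on top, gives 66 + 6.6 = 72.6 after one round, or 66/0.90 = 73.3 if replacements who drop out are also replaced. Both exceed the stated maximum, so that reading contradicts the plan's wording. On the reading that fits, the six places beyond 60 are the drop-out allowance, used once.

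**Effect on 33 per group.** Suppose 60 are randomised 30:30 and six drop out and are replaced in the same arm.

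- P(3:3 split, giving 33 vs 33) = C(30,3)² / C(60,6) = 0.329
- P(4:2 either way, giving 34 vs 32) = 2 × C(30,4) × C(30,2) / C(60,6) = 0.476

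To see what 34 versus 32 means for safety, take the two-sided 95% upper bound for an AE seen in no subject, 1 − 0.025^(1/n):

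| n dosed | upper bound |
|---|---|
| 32 | 10.9% |
| 33 | 10.6% |
| 34 | 10.3% |

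The imbalance moves this bound by about 0.3 percentage points.

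**Share of allocations affected.** Within the cap, on the 60-then-6 sequence, at most 6/66 = 9.1% of subjects have an arm set by an earlier drop-out. The cap would stop full replacement fairly often: P(more than 6 of 60 drop out) = 0.394. On the on-top reading, 6.6/72.6 = 9.1% is an expected share and not a ceiling, since P(7 or more of 66 drop out) = 0.494. Neither figure is a disclosure rate; the documents give no unblinding rate.

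**What removing the rule would cost.** Without replacement, completers per arm follow Bin(33, 0.90).

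- Mean 29.7, SD √(33 × 0.9 × 0.1) = 1.72, 95% range 26 to 33
- P(at least 30 in one arm) = 0.577; in both arms 0.577² = 0.333
- P(at least 60 of 66 in total) = 0.506

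The last figure depends heavily on the drop-out rate, which is only an estimate:

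| drop-out | expected completers of 66 | P(at least 60) |
|---|---|---|
| 5% | 62.7 | 0.954 |
| 10% | 59.4 | 0.506 |
| 15% | 56.1 | 0.116 |
| 20% | 52.8 | 0.014 |

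**The blinding route.** An arm fixed in advance does harm only if those who enrol or assess the subject can predict it. That needs four things together: an individual unblinding, which section 6.5.2 restricts and says is not routine for AEs; a decision to use the optional replacement; a replacement recruited at the same one of up to twelve sites; and staff who recognise the new subject as that replacement. If any link is missing, the replacement receives an assignment that blinded staff cannot tell from any other.

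**The case for a change.** The best argument for a change is that the text is incomplete and easily repaired. Sites and the IWRS programmer need the allocation rule during recruitment, so a later SAP is no place to settle it. Nothing states what triggers replacement, who decides, or that sites are kept unaware that a subject is a replacement. Section 6.5.2 directs the very subjects whose arm may be known towards early withdrawal. The primary analysis also does not depend on the rule, because dosed drop-outs stay in the Safety Population and no completer population exists.

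Part of this stands. The documents do not describe how a replacement's arm is assigned or concealed, and a sentence on it would be tidy. But section 5.3 already requires IWRS assignment and a blinded study team without exempting replacements, so blind assignment of replacements is the natural way to build the system. Section 6.5.2 also relies on an Unblinding Plan that is not among the documents, so silence here does not show that a safeguard is missing.

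The claim that replacement gains nothing for safety goes too far. Subjects randomised but never dosed fall outside the Safety Population, and the safety assessments at days 56 and 90 need subjects who are still being followed.

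**Conclusion.** No change follows. Same-arm replacement is an optional way to protect the stated 30 completers per group, which 66 subjects without replacement would reach in both arms only about one time in three at 10% drop-out. Its price is that group sizes are approximate, most often 34 versus 32 or 33 versus 33 on the 60-then-6 sequence, and that up to about 9% of allocations follow an earlier drop-out. The enrolment definition in section 5.3 keeps replacements within the 66. With dosed drop-outs retained in the Safety Population and no formal comparison, no test, error rate or conclusion is shown to change, and following the plan as written gives sound descriptive results. The unstated details (blind assignment of replacements, 33 per group as approximate) are ones that a competent IWRS set-up and analyst would fill in the same way.

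This rests on equal, independent drop-out of 10% and on replacements being assigned through the IWRS under the general blind of section 5.3. Evidence that sites were told which subject a newcomer replaced, after an unblinding at that site, would reopen the question.

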#### **8.1.3 Analysis Populations**

There are three analysis populations: Safety, modified Intention-to-treat (mITT), and Pharmacodynamics (PD).

##### **8.1.3.1 Safety Population**

All randomized subjects who receive any amount of study treatment will be included in the Safety Population. Subjects will be summarized according to the treatment they actually received. Demographic, baseline characteristics, plasma concentrations of DM199, and Safety analysis will be conducted using the Safety Population.

##### **8.1.3.2 Modified Intention-to-Treat (mITT) Population**

All randomized subjects who receive at least one dose of study treatment and who have at least one post-dose efficacy assessment will be included in the mITT population. Subjects will be

summarized according to the treatment they are randomized to receive. Efficacy analysis will be conducted using the mITT population.

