### 5.12 NIH STROKE SCALE

For subjects undergoing reperfusion treatment prior to study enrollment the NIH stroke scales (NIHSS) must occur at least one hour after treatment. The scale will also be administered at days 22 and 90.

A NIHSS of  $\geq 6$  and  $\leq 25$  at enrollment is required for study inclusion.

The NIHSS will be administered by the Investigator or a designated and trained member of the study team.

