#### *8.1.3.3 Pharmacodynamic Population*

Randomized subjects who receive study medication and have sufficient plasma concentration for analysis of the PD endpoints will be included in the pharmacodynamic analysis. Subjects with protocol violations will be assessed on a subject-by-subject basis for inclusion in the PD population. PD analysis will be conducted using the PD population.

Any additional analysis populations will be detailed in the Statistical Analysis Plan (SAP).

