#### **8.3.2.1 Adverse Events/Serious Adverse Events**

Adverse events (AEs) will be coded using the Medical Dictionary for Regulatory Activities (MedDRA®) and data will be summarized by System Organ Class (SOC) and Preferred Term (PT). The number and percent of subjects reporting each AE will be summarized for each treatment group and overall. A subject with two or more AEs within the same level of summarization (i.e., SOC or PT) will be counted only once in that level using the most severe (i.e., highest severity/grade) event or most related (for the relationship to study treatment table). Percentages will be based on the number of subjects in the Safety Population within each treatment group. The number of AEs reported will also be presented.

Treatment-emergent AEs (TEAEs) are defined as pre-treatment existing conditions that worsen after study treatment administration, or events that occur during the course of the study during or after administration of study treatment. Only TEAEs will be included in the AE summary tables which will present data by treatment group. In the case of a missing AE start date or stop date, the most conservative approach will be followed.

An overall summary of AEs will be produced including the number of TEAEs; the number and % of subjects reporting at least one: TEAE, serious TEAE, grade 3 or higher TEAE, TEAE related to study treatment (possible, probable), serious TEAE related to study treatment, grade 3 or higher TEAE related to the study treatment, TEAEs by maximum severity and TEAEs by maximum relationship, as appropriate.

Additional AE tables will be generated as follows, as appropriate:

- Overall TEAEs by SOC and PT
- TEAEs by Maximum Severity
- TEAEs by Maximum Relationship to Study Treatment
- Treatment Emergent SAEs

- TEAEs with Grade 3 or Higher
- Study Treatment Related TEAEs by SOC and PT
- Study Treatment Related TEAEs by Maximum Severity

A by-subject AE data listing, including verbatim term, MedDRA SOC and PT, severity, outcome and relationship to study treatment, will be provided. A separate listing will be generated for SAEs.

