### **8.3.4 Efficacy Endpoints**

Efficacy endpoints will be analyzed using the mITT population.

Efficacy endpoints (continuous variables) will be summarized using descriptive statistics for each treatment group for all time points assessed, including change from baseline for all post-dose assessments (days 22 and 90), as applicable.

In addition, categorical variables, including the total NIH Stroke Scale score indicating stroke severity, will be summarized using frequency counts and percentages, for each treatment group and all time points assessed, as applicable.

Any additional efficacy analyses will be described in the SAP, as applicable.

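### The efficacy set requires a post-dose assessment, first scheduled at Day 22, and no rule says how deaths enter the stroke scales, so the efficacy summaries as written describe only subjects alive and assessed

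*Combined protocol and SAP*

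**What the plan says.** - **Efficacy set (8.1.3.2).** Randomised subjects with at least one dose "who have at least one post-dose efficacy assessment will be included in the mITT population". They are grouped as randomised. Section 8.3.4 names no other set for efficacy.
- **Timing (Table 1; 5.12 to 5.14).** NIHSS, Barthel and mRS are taken at baseline and next at Day 22. For the NIHSS, 5.12 states: "The scale will also be administered at days 22 and 90". Table 1 also marks all three scales at the Early Withdrawal visit.
- **Missing data (8.3).** "Imputation: No missing data will be imputed generally". The bullet goes on to concentrations below the quantification limit and gives no exception for death.
- **Summaries (8.3.4).** Continuous scores get descriptive statistics and change from baseline. In addition, "categorical variables, including the total NIH Stroke Scale score indicating stroke severity, will be summarized using frequency counts and percentages". No denominator is named beyond the mITT set. The adverse-event section does name one: "Percentages will be based on the number of subjects in the Safety Population within each treatment group" (8.3.2.1).
- **Death.** It appears in the SAE definition (6.2.2), AE follow-up (6.3.3), pregnancy reporting (6.3.4), post-study events (6.3.5) and Grade 5 in Table 4. It is not linked to an efficacy scale anywhere.
- **Deferral.** "Detailed statistical methods will be provided in a separate Statistical Analysis Plan (SAP) prior to data base lock" (8.3) and "Any additional efficacy analyses will be described in the SAP, as applicable" (8.3.4). Section 8.1.3.3 also leaves any additional analysis populations to the SAP. That SAP is not in the supplied document.

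**The concern.** Membership of the efficacy set depends on something that happens after randomisation and that treatment could affect. A subject must survive to be scored. Entry allows an NIHSS of up to 25 (3.1), so deaths before Day 22 or Day 90 should be planned for.

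If deaths fall mainly among subjects with a poor prognosis, those left to be assessed look better, and the arm with more deaths can look better on function. If deaths are unrelated to prognosis, no false benefit is expected, but the functional tables still leave out the mortality. No formal comparison is planned, so readers will judge efficacy from these tables directly, and what the percentages are percentages of then matters.

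**Working it through.** **1. What the stated rules do with each case**

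| Case | In mITT? | Day 22 value | Day 90 value |
|---|---|---|---|
| Dosed, dies before any post-dose assessment | No | None | None |
| Assessed at Day 22, dies before Day 90 | Yes | Yes | None |
| Withdraws alive early, attends the withdrawal visit | Yes | Use of that score not stated | Use of that score not stated |

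The third route is closed to a subject who dies. The first two rows assume that death is not itself recorded as an mRS value. Section 5.14 gives no mRS levels, so the documents do not settle this.

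**2. The plan's own numbers (8.1.2)**

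60 × 1.10 = 66 enrolled, or 33 per arm. Dividing instead, 60 / 0.90 = 66.7, and 66 × 0.90 = 59.4 completers. The stated figure is therefore reproduced to within a subject. The 33 is an enrolled number. Below I assume that all 33 are dosed and ignore replacement of drop-outs.

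**3. Effect on one arm's percentage**

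The plan gives no death rates and no outcome cut, so these counts are assumed. With d early deaths and x subjects in a category, the percentage is x/(33 − d) among those assessed and x/33 among all dosed. The ratio 33/(33 − d) is 1.03, 1.06 or 1.10 for d = 1, 2 or 3. Three deaths would use the arm's whole drop-out allowance (33 − 30 = 3) if deaths count as drop-outs, which is not stated.

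For d = 3, the SE of an arm difference at the planned 30 completers per arm is √(2p(1 − p)/30), with p the percentage among those assessed:

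| x | Of assessed | Of all dosed | Shift (points) | SE (points) | Shift/SE |
|---|---|---|---|---|---|
| 6 | 6/30 = 20.0% | 6/33 = 18.2% | 1.8 | 10.3 | 0.18 |
| 12 | 12/30 = 40.0% | 12/33 = 36.4% | 3.6 | 12.6 | 0.29 |
| 18 | 18/30 = 60.0% | 18/33 = 54.5% | 5.5 | 12.6 | 0.43 |

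The last column describes a between-arm distortion only if all 3 deaths fall in one arm. With 3 deaths and the same x in both arms, the difference is zero on either denominator.

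**4. Direction, with unequal deaths (assumed 3 against 7, all early)**

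- *Deaths related to prognosis.* Suppose 12 of 33 are in a favourable category in each arm. Among those assessed: 12/30 = 40.0% against 12/26 = 46.2%. The arm with 7 deaths looks 6.2 points better. Of all dosed: 36.4% in both.
- *Deaths unrelated to prognosis.* Suppose about 40% of those assessed are favourable in each arm. Among those assessed: 12/30 = 40.0% against 10/26 = 38.5%, a gap of 1.5 points that comes from rounding to whole subjects. Of all dosed: 36.4% against 10/33 = 30.3%, a gap of 6.1. There is no false benefit, but the mortality difference disappears from the table.

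**5. Day 90 denominator**

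Take 1 death before Day 22, 2 deaths between Days 22 and 90, and 12 subjects in a category at Day 90. The result is 12/33 = 36.4% of all dosed, 12/32 = 37.5% of the mITT set, or 12/30 = 40.0% of those with a value. Section 8.3.4 does not say whether the mITT number or the number with a value is the base.

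**The case against.** **The SAP may settle it.** Detailed methods, further efficacy analyses and additional populations are all deferred there, and an all-dosed efficacy set could be added without amending 8.1.3.2. This stands as a limit on the claim: a reader might infer that the trial's efficacy analysis will be survivor-only, and the documents cannot show that. They show that the stated rule has this effect and that no supplied text counters it. The deferral promises additions in general terms and does not itself supply a rule for deaths.

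**A death might be scored on the mRS.** If so, that value might count as a post-dose efficacy assessment and keep the subject in the set. This is possible, but no section says it, and it would leave NIHSS and Barthel unaddressed.

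**Deaths are already visible.** They are. Fatal events must be documented (6.2.2), Grade 5 falls within the Grade 3 or higher table, and listings carry outcome (8.3.2.1). It would be wrong to infer that the plan hides deaths. What is missing is the link to the functional tables. The safety tables group subjects as treated and the efficacy tables as randomised, so the two need not line up.

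**The mITT condition barely matters for two of the three scales.** This is correct. Subjects without post-dose scores add nothing to post-dose NIHSS or Barthel means, so removing the condition leaves those means unchanged. It alters categorical denominators and baseline rows.

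**Efficacy is secondary.** The only objective is safety and tolerability (2.1), and 8.3 rules out formal comparisons. This stands and limits the weight of the point.

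**Conclusion.** The point holds in conditional form and should be fixed. As written, a membership rule makes the efficacy summaries conditional on being alive and assessed, unless a death is recorded as an mRS value or the SAP adds a rule. Such summaries can flatter the arm with more deaths.

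The size is modest. In the central illustration the shift is 3.6 points, about 0.3 SE of the arm difference. That rests on assumed counts, on all 33 enrolled per arm being dosed, and on all 3 deaths falling in one arm. Balanced deaths with similar outcome rates would largely cancel.

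A reader might go further and infer a bias towards DM199. Nothing supports that: the documents give no death rates and no reason to expect more deaths in either arm. The unstated percentage denominator is, taken alone, only missing detail.

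**What to change.** Before unblinding:

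1. In 8.3.4 and the SAP, report the mRS as a full distribution at Days 22 and 90 in all randomised subjects who received any study treatment, analysed as randomised. Show known deaths as a separate worst category and missing values separately.
2. To allow this, either delete the post-dose-assessment condition in 8.1.3.2 or define that all-dosed efficacy set in the SAP.
3. Beside the NIHSS and Barthel summaries, show deaths by arm at each visit, and label those summaries as conditional on being alive and assessed.

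The cost is a few sentences and a few table rows, with no extra visit. Summaries may look less favourable in whichever arm has more deaths. Some deaths after withdrawal may stay unknown, because AE collection runs to withdrawal (Table 1, note 11) and later events need not be actively sought (6.3.5). Supervision after a medical withdrawal (5.15), AE follow-up (6.3.3) and notification of related post-study SAEs, including death (6.3.5), would recover some of them.
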